#### 3.4.1.9 Time to Disease Assessments

Time to Disease Assessments (TDA) is defined as the time from randomization (dose expansion) / the first dose of IP (dose escalation) first dose of IP until each disease assessment, regardless of evaluability. TDA is defined in days as follows:

TDA (days) = (Date of disease assessment – Date of randomization (dose expansion) / the first dose of IP (dose escalation) first dose of IP+ 1).

The median TDA and its 95% CI will be estimated using the Kaplan-Meier method for the first 4 post-baseline disease assessments. For disease assessments that span multiple days, the disease assessment date assigned for the TDA analysis will be the date when the first imaging scan from the disease assessment was performed.

## 3.4.2 Additional Analyses of the Efficacy Endpoints

Disease Response will also be assessed based on an application of immune-related Response Evaluation Criteria in Solid Tumors (irRECIST) (Nishino et al, 2013) to investigator assessed tumor measurements. All new lesions meeting measureable criteria will be included in the Tumor Burden. Objective Response by irRECIST is defined as immune-related complete response (irCR) or immune-related partial response (irPR) with confirmation required occurring no fewer than 4 weeks after initial documentation of irCR or irPR. If an irPR or irCR that is pending confirmation is designated at an assessment followed by 1 or more non-evaluable assessments or assessments of irSD, response may be confirmed thereafter Disease Control - 8 by irRECIST is defined as confirmed irCR, confirmed irPR, or immune-related stable disease (irSD) (maintained for ≥ 8 weeks). A similar definition applies

to Disease Control - 24. Duration of irSD is defined as the time from randomization (dose expansion) / the first dose of IP (dose escalation) until the first documentation of disease progression or death due to any cause, whichever occurs first, and will allow for the protocoldefined disease assessment window of 3 days. Concordance/discordance between RECIST 1.1 and irRECIST disease assessment will be summarized in frequency table.

## 3.4.3 Subgroup Analyses

No subgroup analyses are planned.

## 3.3.5 Response Derivations and Handling of Missing Data

Guidance regarding the handling of dropouts and missing data will apply uniformly to all efficacy analyses resulting from an application of RECIST 1.1 and irRECIST to investigator assessed tumor measurements. For investigator reported outcomes, analyses will present outcomes reported by the investigator without consideration of missing data or censoring rules.

#### 3.3.5.1 RECIST 1.1 Derivations

#### **DERIVATION OF TARGET LESION RESPONSE**

Target lesion response will be programmatically derived on the data collection instrument once RECIST 1.1 criteria are applied to the site personnel recorded target lesion measurements.

Possible values include:

- CR Complete Response
- PR Partial Response
- SD Stable Disease
- PD Progressive Disease
- NE Non-evaluable
- NA Not Applicable (set value for all post-baseline disease assessments only if no target lesions are identified at baseline)

The derivation for target lesion response is as follows (please note the order of the algorithm below is important):

- 1. If "Any Target Lesions Present" equals "No" on the *Target Lesions Baseline* CRF, then all post-baseline "Target Lesion Response" equals "NA".
- 2. Else, if "Percent Change from Nadir Sum of Diameters" is greater than or equal to 20% and the absolute increase from the nadir (defined as the "Total" for each post-

- baseline disease assessment minus the "Nadir Sum of Diameters") is greater than or equal to 5 mm, then "Target Lesion Response" equals "PD".
- Else, if "Not Done" is selected, or "Measurement" is left blank, or "Lesion no longer Measureable" is selected and equal to "NE", or "Lesion Intervention" is selected for any Target Lesion identified at Baseline, then "Target Lesion Response" equals "NE".
- 4. Else, if "Total Non-Lymph Node" equals "0" and all Lymph Node Target Lesion "Measurements" are less than "10" individually, then "Target Lesion Response" equals "CR".
  - a. Note: This step requires examining "Measurements" separately for Target Lesions with "Lymph Node" equal to "Yes" and "No".
- 5. Else, if "Percent Change from Baseline Sum of Diameters" is less than or equal to 30%, then "Target Lesion Response" equals "PR".
- 6. Else, "Target Lesion Response" equals "SD".

If a subject has a missing tumor measurement at a disease assessment for 1 or more target lesions, the sum of diameters (longest for non-nodal lesions, short axis for nodal lesions) will be reported for the remaining target lesions. These data will be used to indicate radiologic disease progression if the sum of diameters for the observed lesions increases at least 20% from the nadir sum of diameters of all lesions and demonstrates at least a 5 mm absolute increase from the nadir sum of diameters of all lesions, in spite of the missing data (or if other criteria for PD are met).

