#### 3.4.1.1 Best Overall Response

Best overall response (BOR) will be based on all post-baseline disease assessments that occur prior to the initiation of subsequent anticancer treatment. If re-treatment is permitted following an initial disease progression, a BOR will be reported separately for the re-treatment period. BOR will be summarized with the number and percentage of subjects for

the following categories: complete response (CR); partial response (PR); stable disease (SD); progressive disease (PD); and non-evaluable (NE).

At least 6 weeks from randomization (dose expansion) / the first dose of IP (dose escalation) first dose of IP must elapse without a radiological disease progression in order to assign a best overall response of SD. The definition of 6 weeks will allow for the protocol-defined disease assessment window of 3 days. Confirmation of PR and CR is required and must occur no fewer than 4 weeks after initial documentation of PR or CR. If a PR or CR that is pending confirmation is designated at an assessment followed by 1 or more non-evaluable assessments for CR or 1 or more non-evaluable assessments or assessments of SD for PR, response may be confirmed thereafter. Confirmation of PD is required in the dose escalation phase, but not the dose expansion phase. A confirmed PD will be a documented occurrence of a PD that is confirmed by a consecutive repeat assessment no fewer than 4 weeks later. A PD that occurs without follow-up scans to provide confirmation or only non-evaluable follow-up scans will also be considered a "confirmed" PD.

Concordance/discordance of disease assessment by investigator and derived disease assessment will be summarized in frequency table.

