#### 3.4.1.8 Change from Baseline in Tumor Sizes

The percent change from baseline in target lesion sum of diameters (longest for non-nodal lesions, short axis for nodal lesions) will be calculated at each post-baseline disease assessment with recorded measurement for all target lesions defined at baseline. The percent change from baseline in target lesion sum of diameters is defined as follows:

100 \* ( $\Sigma$  Diameters at DA X -  $\Sigma$  Diameters at BL) / ( $\Sigma$  Diameters at BL).

The percent change from baseline in target lesion sum of diameters will be presented by subject using spider plots. The best percent change from baseline in target lesion sum of diameters is defined as the largest reduction or smallest increase (in the case where a reduction does not occur) from baseline observed over all post-baseline disease assessments. The best percent change from baseline will be presented using waterfall plots. Target lesion measurements and sum of diameters will be listed by disease assessment and subject.

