#### 3.3.5.2 irRECIST Derivations

#### **DERIVATION OF TUMOR BURDEN RESPONSE**

Tumor burden will be programmatically derived on the data collection instrument once irRECIST criteria are applied to the site personnel recorded target lesion and new lesions included in tumor burden measurements.

- irCR Complete Response
- irPR Partial Response
- irSD Stable Disease
- irPD Progressive Disease
- irNE Non-evaluable
- irNA Not Applicable (set value for all post-baseline disease assessments only if no target lesions are identified at baseline)

The derivation for tumor burden response is as follows (please note the order of the algorithm below is important):

- 1. If "Any Target Lesions Present" equals "No" on the *Target Lesions Baseline* CRF, then all post-baseline "Tumor Burden Response" equals "irNA".
- 2. Else, if "Percent Change from Nadir Sum of Diameters" is greater than or equal to 20% and the absolute increase from the nadir (defined as the "Total" for each Post-Baseline DA minus the "Nadir Sum of Diameters") is greater than or equal to 5 mm, then "Tumor Burden Response" equals "irPD".
- 3. Else, if "Not Done" is selected, or "Measurement" is left blank, or "Lesion no longer Measureable" is selected and equal to "NE", or "Lesion Intervention" is selected for any target lesion identified at baseline or new lesions included in the tumor burden, then "Tumor Burden Response" equals "irNE".
- 4. Else, if "Total Non-Lymph Node" equals "0" and all lymph node target lesion and new lesion included in the tumor burden "Measurements" are less than "10" individually, then "Tumor Burden Response" equals "irCR".
- a. Note: This step requires examining "Measurements" separately for Target lesions and new lesion included in the tumor burden with "Lymph Node" equal to "Yes" and "No".
- 5. Else, if "Percent Change from Baseline Sum of Diameters" is less than or equal to 30%, then "Tumor Burden Response" equals "irPR".
- 6. Else, "Tumor Burden Response" equals "irSD".

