Decision matrices for continuous monitoring of ORR  $\delta$  at the prespecified MEDI0680/durvalumab combination sample sizes for interim futility assessments are presented in Figure 4-1. The matrices presented are examples and assume that the MEDI0680/durvalumab combination treatment group will randomize in a 2:1 ratio to the nivolumab treatment group. Additional decision matrices will be prepared as needed to accommodate observed data. Futility, continuation, and efficacy decisions are marked using red, yellow, and green cells, respectively, and allow for an evaluation of varying combinations of responses between the two treatment groups. The target  $\delta$  was set so as to demonstrate a 20% increase in the MEDI0680/durvalumab combination ORR over the benchmark nivolumab ORR based on investigator assessments, in a similar RCC population (ORR = 25.1 [95% CI: 21.0%, 29.6%]; Motzer et al, 2015). Given assumptions of a benchmark ORR in the nivolumab treatment group of 25% and a true  $\delta$  = 20%, darker color cells represent scenarios that would be observed in practice with a 95% likelihood.

For example, given a target  $\delta$  of 20% and assuming 3 observed responders in the nivolumab treatment group after 10 subjects have reached their second post-baseline disease assessment or have completed the study, observing 4 or fewer responders after 20 subjects in the MEDI0680/durvalumab combination have reached their second post-baseline disease assessment or have completed the study would trigger stopping enrollment claiming futility due to a high probability of reaching a NoGo decision upon enrollment to 60 subjects given the existing observed data Figure 4-2flo and Table 4.1).

A false negative is defined as observing either futility criteria during the continuous monitoring stage or NoGo criteria upon enrollment of 60 subjects in a given treatment group when the true ORR  $\delta$  is greater than or equal to the target  $\delta$  (ie, False Negative: P[NoGo Decision | True  $\delta \geq$  Target]). Assuming a true  $\delta$  of 20%, the false negative rate is 11% (see highlighted cell in Table 4.1 below). Assuming a true  $\delta$  of 25%, the false negative rate is 5%. Additionally, assuming a true  $\delta$  of 20%, the Go decision rate (efficacy decision during the continuous monitoring stage or a Go decision upon enrollment of 60 subjects) is 37% with confirmation at the final analysis 75%.

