Upon enrollment of 60 subjects in the dose-expansion phase, a final analysis will be performed. NoGo criteria will be met if the probability that the  $\delta$  exceeds the pre-specified

[figure not shown]
target of 20% is less than 10% (ie, NoGo:  $P[\delta > Target] < 10\%$ ). Go criteria will be met if the probability that the  $\delta$  exceeds the pre-specified target of 20% is more than 70% (ie, Go:  $P[\delta > Target] > 70\%$ ). For futility analyses, a response is defined as either a confirmed or unconfirmed CR or PR as per RECIST 1.1 and for the final analysis a response is defined as a confirmed CR or PR as per RECIST 1.1.

At interim analyses, efficacy and selected safety data will be summarized to assess the overall benefit-risk profile. The analysis populations to be used for the interim analysis are described below:

- As-treated with 17 weeks of potential follow up is defined as all subjects in the Astreated Population who have a baseline disease assessment and have an opportunity to be followed for at least 17 weeks (i.e., received the first dose of MEDI0680, durvalumab or nivolumab, whichever earliest, at least 17 weeks ago). The 17 weeks are to have at least 2 post-baseline disease assessments plus the one week visit window. This is the primary analysis population for the interim analysis of efficacy data.
- Response evaluable with 17 weeks of potential follow up is defined as all subjects in the As-treated Population who 1) have a baseline disease assessment; 2) have an opportunity to be followed for at least 17 weeks; and 3) have any post-baseline disease assessments or experience clinical PD/death. This is the secondary analysis population for the interim analysis of efficacy data.
- As-treated with 9 weeks of potential follow up is defined as all subjects in the Astreated Population who have a baseline disease assessment and have had an opportunity to be followed for at least 9 weeks. The 9 weeks are to have at least 1 post-baseline disease assessments plus one week visit window. This is the exploratory analysis population for the interim analysis of efficacy data.
- **As-treated Population**, as defined in section 3.2, is the primary analysis population for the interim analysis of safety data.

Figure 4-1 Decision Matrices for Continuous Monitoring

(MEDI0680 + Durvlumab vs Nivolumab: 10% false negative if effect = 20%)

[figure not shown]
[figure not shown]

Figure 4-2 Visual Joint Predictive Probability Operating Characteristics

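### Does step 5 of the SAP's response algorithms really count stable disease as partial response because the 30% cut-off has no minus sign?

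*SAP*

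**What the plan says.** SAP section 3.3.5.1 derives target lesion response in a fixed order: not applicable, PD, NE, CR, PR, then SD as the remainder. PD needs an increase of at least 20% and at least 5 mm over the nadir. Step 5 then reads "Percent Change from Baseline Sum of Diameters' is less than or equal to 30%, then 'Target Lesion Response' equals 'PR". Section 3.3.5.2 has the same step for tumor burden: "Percent Change from Baseline Sum of Diameters' is less than or equal to 30%, then 'Tumor Burden Response' equals 'irPR".

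Section 3.4.1.8 gives the formula for percent change as the sum at the assessment minus the sum at baseline, divided by the sum at baseline. It puts shrinkage and growth on one signed scale, with the best change being the "largest reduction or smallest increase (in the case where a reduction does not occur) from baseline observed over all post-baseline disease assessments".

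Section 3.4.1.1 lets a PR await confirmation across "1 or more non-evaluable assessments or assessments of SD for PR, response may be confirmed thereafter". Section 3.4.1.3 builds DCR8 and DCR24 on maintained SD, and the table of derived disease response in section 3.3.5.1 has an SD row. In section 4, "For futility analyses, a response is defined as either a confirmed or unconfirmed CR or PR as per RECIST 1.1".

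**The concern.** On a signed scale, a ceiling of +30% for PR takes in unchanged tumors, small shrinkage and moderate growth. Since PD is removed earlier and SD is only the remainder, SD would almost vanish. Reading the field as an unsigned decrease does not help: small shrinkage would then be PR and large shrinkage SD.

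Section 3.3.5.1 says the response is derived by program, so the text serves as a coding specification. Its result feeds disease response, best overall response and ORR. The futility analyses count unconfirmed responses, so a single stable scan could count as one. An error of this kind would affect the primary endpoint of the expansion phase in both arms.

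**Working it through.** **1. What the printed rule would do.** Inputs are the PD rule and step order of section 3.3.5.1 and the formula of section 3.4.1.8, with complete measurements and no nodal targets. Let B be the baseline sum, N the nadir and C the current sum. Take B = N = 50 mm.

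- PD: C ≥ 1.20 × 50 = 60 mm, an increase of 10 mm, which also meets the 5 mm condition.
- PR with +30%: C ≤ 1.30 × 50 = 65 mm. After PD is removed, this leaves 1 to 59 mm, and no SD.
- PR with -30%: C ≤ 0.70 × 50 = 35 mm. SD is then 36 to 59 mm.

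In general, SD under the printed rule needs C > 1.30 × B. With N ≤ B this already exceeds 1.20 × N, so PD is avoided only if C - N < 5 mm. As C - N ≥ C - B > 0.30 × B, it follows that 0.30 × B < 5, so B < 16.7 mm. SD would be confined to very small baseline sums.

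**2. Which cut-off the rest of the SAP presupposes.**

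| Place in the SAP | Use of SD | With +30% | With -30% |
|---|---|---|---|
| 3.4.1.1 | SD may fall between a PR and its confirmation | almost never possible | works |
| 3.4.1.3 | DCR8 and DCR24 count maintained SD | SD part almost empty | works |
| 3.3.5.1, disease response table | row from target SD to overall SD | almost never used | works |

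Sections 2.1.1, 3.4.1 and 4 also name RECIST 1.1 as the governing criteria. Every other use of the category agrees with a decrease of at least 30%.

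**3. Whether the sign could have been lost in reading.** The machine-read text has *protocoldefined* in section 3.4.2 and *Astreated* in section 4, although both terms are hyphenated elsewhere in the SAP. That fits a hyphen dropped when a line ended on it. On the pages of the algorithm itself, the value lists show no separator between code and meaning, and the number of step 3 is missing.

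Line widths can be compared under an assumption of 12-point Times:

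- step 5 up to and including a minus sign: about 401 pt;
- the same line with -30% and its comma: about 426 pt;
- the section 4 line ending in the broken As-treated: about 400 pt;
- the step 2 line ending in the broken post-baseline, at a page change: about 399 pt.

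A break directly after the minus sign therefore falls where lines of this kind of list are seen to end, and the sign would be dropped like the other two. Step 5 in section 3.3.5.2 opens with identical words and would break at the same point. Its agreement is not independent evidence that the sign is absent from the plan.

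**4. The supposed effect on the futility rule.** Section 4 gives a worked example with 3 of 10 nivolumab responders, in which "observing 4 or fewer responders after 20 subjects in the MEDI0680/durvalumab combination have reached their second post-baseline disease assessment" leads to a stop. NoGo is P(δ > 20%) < 10% at 40 versus 20 subjects, and futility is a predictive probability of NoGo above 0.90. The SAP states no prior, so Beta(1,1) and Beta(0.5,0.5) are assumed.

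| Combination | Nivolumab | Beta(1,1) | Beta(0.5,0.5) | Stop? |
|---|---|---|---|---|
| 4/20 | 3/10 | 0.947 | 0.934 | yes, as in the SAP |
| 5/20 | 3/10 | 0.860 | 0.831 | no, as in the SAP |
| 8/20 | 5/10 | 0.852 | 0.849 | no |
| 10/20 | 6/10 | 0.841 | 0.845 | no |
| 12/20 | 7/10 | 0.844 | 0.852 | no |
| 8/20 | 6/10 | 0.960 | 0.961 | yes |
| 7/20 | 5/10 | 0.927 | 0.924 | yes |
| 8/20 | 4/10 | 0.639 | 0.618 | no |

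The first two rows reproduce the SAP's boundary. Rows three to five add an assumed stable-disease share of 20%, 30% or 40%, equal in both arms (for 20%: 4 + 4 = 8 of 20 and 3 + 2 = 5 of 10). The last three rows move one subject from the 8/20 versus 5/10 case. One more counted nivolumab subject, or one fewer combination subject, restores the stop. Without a stable-disease rate in the SAP, neither size nor direction can be stated.

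**The case for a change.** The strongest case for the concern is that the printed words are what they are, twice, and nothing else in the SAP states the PR cut-off as a decrease. Many short marks did survive: the minus in the formula of section 3.4.1.8, the hyphens in Non-CR/Non-PD, and the line-end hyphen in step 2. If the sign were truly missing and the program followed the text, ORR would be inflated in both arms. The concordance table of section 3.4.1.1 would show the problem but not correct it.

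Part of this stands. The classification arithmetic is correct, and the machine-read text cannot prove that the sign is in the source. But the marks inside a line say nothing about those at a line end, and the step 2 hyphen stands at a page change, where the two line pieces were not joined. The objection shows what would follow if the sign were absent. It does not show that it is absent, and the concern depends on that.

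**Conclusion.** The concern does not hold as a finding against the plan. It needs the minus sign to be missing from the SAP itself or from the derivation program, and the documents do not show this. The pattern of lost hyphens, the likely line break in step 5 and the SAP's consistent use of SD all favor a -30% cut-off whose sign was lost in reading.

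Had the sign really been absent, SD would be limited to baseline sums below 16.7 mm (taking the nadir to be no larger than baseline), which would be serious. The claim that the futility stop would then fail is not supported in any case: the predictive probability of NoGo ranges from 0.62 to 0.96 with small changes in the assumed counts.

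The conclusion rests on the assumed typeface for the line-width comparison, on assumed priors and stable-disease counts for the futility figures, and on the internal consistency of the SAP, which carries the most weight.

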#### **DETERMINATION OF NON-TARGET LESION RESPONSE**

Non-target lesion response will be assigned by site personnel following a qualitative overall assessment of all non-target lesions.

- CR Complete Response
  - O Disappearance of all non-target lesions and normalization of tumor marker level. All lymph nodes must be non-pathological in size (<10mm short axis)
- Non-CR/Non-PD Non-Complete Response / Non-Progressive Disease
  - Persistence of one or more non-target lesion(s) and/or maintenance of tumor marker level above the normal limits
- PD Progressive Disease
  - o Unequivocal progression of existing non-target lesions.
- NE Non-evaluable
- NA Not Applicable (set value for all post-baseline disease assessments only if no non-target lesions are identified at baseline)

Though non-target lesion responses are a subjective decision made by the site personnel, certain responses may be limited depending on the non-target lesion statuses recorded. An algorithm is provided below highlighting appropriate possible non-target lesion responses based on recorded data. Reaching a red box (•) signifies having reached the only allowable non-target lesion responses based on non-target lesion statuses. Reaching a green box (•) signifies having reached the end of the algorithm and more than one possible non-target lesion response is possible from which the Investigator may choose.

- 1. a) If no non-target lesions are identified at baseline, all post-baseline non-target lesion responses should equal NA.
  - b) Else, if any non-target lesions are identified at baseline, responses may be limited to CR, Non-CR/Non-PD, PD, NE (ie, responses of NA are not permitted). Go to Rule 2.
- 2. a) If all non-target lesions have a status are "Absent", the responses may be limited to CR.
  - b) Else, if at least one non-target lesion status is NOT "Absent", the responses may be limited to Non-CR/Non-PD, PD, NE (ie, responses of CR, NA are not permitted). Go to Rule 3.
- 3. a) If all non-target lesions have a status of "Unequivocal Progression", responses may be limited to PD.
  - b) Else, if no non-target lesions have a status of "Unequivocal Progression", responses may be limited to Non-CR/Non-PD, NE (ie, responses of CR, PD, NA are not permitted).

